Potential benefits of intermediate-dose vs. prophylactic dose anticoagulation	
 • Potential for reduced risk of thrombotic complications (including VTE, MI, stroke, and line thrombosis) • Potential for improving the recovery from need from mechanical ventilation. • Potential for reducing the risk of DIC. • Potential for reducing the risk of renal failure. • Potential for reducing mortality as a result of reducing the above components.
Potential risks of intermediate-dose vs. prophylactic dose anticoagulation	
 • Increased risk of bleeding, including major bleeding • Heparin induced thrombocytopenia

VIII. Study Design and Analysis Plan (include timing and primary and secondary endpoint analysis)

In order to assess event rates and appropriately adjust study measures as part of adaptive trial design, a blinded interim analysis at the combined event rate of both study arms will be performed. Once the trial is completed, analysis will be performed by intention to treat.

General Design

This is a cluster randomized-controlled clinical selection trial of interventions for anticoagulation for COVID-19 patients in the ICU. ICU subunits will be randomly assigned to give patients intermediate (higher) dose or prophylactic (lower) dose of anticoagulation. The primary goal of the trial is to select the best intervention with a high probability of *correct* selection if one intervention is truly superior by a pre-specified effect size. Up to 100 patients (with expected sample sizes between 69-75 patients for the most likely scenarios) will be enrolled in the study, using a novel sequential design. Each time an outcome is observed for a patient, those outcomes are added to a running tally of successes for each intervention. There is a pre-specified criterion in terms of the success tallies for selecting arm as evidence of apparent superiority accumulates. With this sequential procedure, the preferred intervention can be selected during the ongoing enrollment as soon as the pre-specified selection criteria are met, and further enrollment will cease. To ensure that there will be some unbiased estimates of the proportion of patients with a good outcome available for each intervention arm, the selection criteria will not be applied until 60 patients have been observed. This novel approach based on the Levin-Robbins-Leu family of sequential selection procedures [18-23].

Study Implementation

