The identification of a preferred treatment will be done using an innovative sequential selection procedure, which will substantially reduce the number of patients in comparison to a hypothesis test procedure. The data will be examined each time a pair of patients completes follow-up after 60 patients have been observed.

The goal of the procedure is to make a correct selection with high probability. The procedure follows the preference zone / indifference zone approach, wherein we require the selection procedure to guarantee a probability of at least 90% *correct* selection (of the truly best intervention), assuming that one is truly superior to the other by a pre-specified amount. This pre-specification defines a region in the parameter space called the *preference zone*. If the best intervention does not exceed the next best by the pre-specified amount, the success probabilities are said to lie in the *indifference zone*, where we shall be indifferent to the fact that the probability of correct selection may be less than 90%. For this trial, the preference zone consists of all parameter vectors (p_1, p_2) of success probabilities where the odds ratio comparing the largest to the next largest is greater than or equal to 2.15 ($p_1=0.35, p_2=0.20$).

The selection procedure is specified by the sampling rule, the stopping rule, and the terminal decision rule, as follows.

Sampling rule: Patients, when eligible, will be enrolled to the study at the “first-come-first-serve” basis. All the participating ICUs can have 2 possible “room type”: negative pressure rooms and non-negative pressure rooms. Each of the participating ICUs will be divided into either two or four clusters as follows. Any ICU with only one room type (i.e., it only has negative pressure rooms or only has non-negative pressure rooms) will be divided into 2 clusters. For ICUs that contain both room types (i.e., it has negative pressure rooms and non-negative pressure rooms), we will divide that ICU into 4 clusters with two clusters for each room type. Two clusters within each ICU and each room type will then be randomized to either of the study arms. Enrolled patients will receive

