the treatment according to the cluster of ICU they are assigned. Post-randomization pairing scheme will be employed to form the pairs if the stopping criterion is not reached at the time that first 60 outcomes have been observed. As the hospital administration changed the room type to accommodate the decrease of COVID patients (e.g., some negative pressure rooms were changed to non-negative pressure rooms), we currently recruitment included more patients in the prophylactic dose group than those of the intermediate dose group. Pending the approval of DSMB, in each ICU and each room type, we will randomize “intermediate dose rooms” and “prophylactic dose rooms” in a 3:1 ratio until we reach enrollment of 30 patients for one group and we will then only assign patients to the other group until we achieve the recruitment of 30 patients that group as well. After we recruit 30 patients for each arm, the ratio of the rooms will be changed back to 1:1 (intermediate vs. prophylactic) for the subsequent recruitment.

Success tallies:

Each time the follow-up for each patient in a pair is complete and a “good” or “poor” outcome is determined for each based on the composite primary outcome, the pair becomes “observed” and is available for sequential monitoring by adding to a running tally of the “good” outcomes for each intervention. These *success tallies* are used for the stopping rule.

Stopping and Decision rule: The criterion for stopping is a *difference of 4 or more between the tallies* if this occurs at or before 60 patients’ outcomes have been observed. At that time, intervention with the largest success tally is selected as the preferred intervention. However, we will not stop the procedure and make a decision before the outcomes of the first 60 patients have become available. In addition, if the criterion for stopping has not been reached at or before 100 outcomes have been observed, the trial will stop by *truncation* with a maximum of 100 patients. At that time, intervention with the largest success tally is selected as the preferred intervention. If there are ties for the largest success tally at time of truncation, we will select the intervention according to other considerations (safety, better secondary outcomes, etc.).

Incomplete pairs:

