The stopping criterion of a lead of at least 4 between largest and smallest success tallies was chosen to achieve a probability of correct selection of at least 90% for any true success probabilities lying in the preference zone characterized by an odds ratio of 2.15 or greater between the true success probabilities of the two interventions. For example, true success probabilities of 0.35 and 0.20 with an odds ratio of 2.15 is lying on the boundary between the preference and indifference zones. For any such configuration with $\{p_1/(1-p_1)\}/\{p_2/(1-p_2)\} = 2.15$, the selection procedure will result in a correct selection with at least 90% probability. Table 1 shows the operating characteristics of the selection procedure under various scenarios of true success probability configurations for the two arms.

TABLE 1
Operating characteristics of the selection procedure

Scenario 1. $p_1=0.35$, $p_2=0.20$, criterion for stopping is a difference of 4 between the tallies, truncation at 100 patients, minimum # of patients before possible selection=60						
ET	EF	PCS	P[truncation]	P[T=T ₀]	P[T=T ₀ ,CS]	P[CS T=T ₀]
68.4	49.6	95.1%	10.2%	62.6%	61.6%	98.4%
Scenario 2. $p_1=0.30$, $p_2=0.20$, criterion for stopping is a difference of 4 between the tallies, truncation at 100 patients, minimum # of patients before possible selection=60						
ET	EF	PCS	P[truncation]	P[T=T ₀]	P[T=T ₀ ,CS]	P[CS T=T ₀]
74.0	55.5.4	87.1%	21.5%	46.6%	44.0%	94.5%
Scenario 3. $p_1=0.20$, $p_2=0.20$, criterion for stopping is a difference of 4 between the tallies, truncation at 100 patients, minimum # of patients before possible selection=60						
ET	EF	PCS	P[truncation]	P[T=T ₀]	P[T=T ₀ ,CS]	P[CS T=T ₀]
83.0	66.4	50.2%	43.5%	25.7%	12.9%	50.2%

ET is the expected total number of patients

EF is the expected total number of patients with bad outcome

PCS is the probability of correct selection

P[truncation] is the probability that the trial will be truncated before reaching the criterion for stopping

P[T=T₀] is the probability of reaching a decision after exactly 60 patients (30 in each arm)

P[T=T₀, CS] is the probability of correct selection after exactly 60 patients (30 in each arm)

P[CS|T=T₀] is the conditional probability that correct selection is made given that exactly 60 patients (30 in each arm)

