For instance, suppose we stop after 60 patients. If the difference between the two groups' success tallies is exactly equal to 4 (the minimum given the design), the likelihood ratio (LR) in favor of having selected the truly better treatment as opposed to having made a mistaken selection equals the odds ratio (OR) raised to the 4th power. Thus, at the design alternative $p_1=0.35$, $p_2=0.20$, the LR would be 21.5. This is usually considered "very strong" evidence. Likelihood ratios in excess of 8 or 10 are generally considered to be moderate to strong evidence [Royall R. Statistical Evidence: A likelihood paradigm. 1997 Chapman and Hall/CRC]. For comparison, the usual "significant at $p < 0.05$ " corresponds to a LR of only 6.8 in large samples. Furthermore, if the design alternative holds, it is highly probable the difference between success tallies will be greater than 4. For example, if the tallies are 11 (about 30×0.35) and 6 ($=30 \times 0.20$), the LR under the design alternative is much larger (46), very strong evidence in favor of a correct selection.

To address the weight of evidence in favor of the maximum likelihood estimate (*mle*) being the true parameters as opposed to the *null* hypothesis $p_1=p_2$ being the true parameters, the generalized LR is 11.2 for the case $T=60$, $X_1=20$, $X_2=10$, which would again be moderate to strong evidence. On the other hand, if $X_1=14$, $X_2=10$, $LR=1.55$, very weak evidence against the null hypothesis. Assuming the trial does not stop at $T=60$, the above LR's will be assessed with the data at the time of selection at the observed *mle*'s for weight of evidence in favor of correct selection and for weight of evidence against the null hypothesis. The assessments will be repeated when all data have been observed, including overrun data coming in after the time of selection.

Minimizing Selection Bias

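### The labelled stopping rule counts a lead of 4 reached at or before 60 outcomes, but the rest of the plan and Table 1 use the current lead at 60 and after each later pair up to 100

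*Combined protocol and SAP*

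**What the plan says.** Section VIII says the procedure is defined by its sampling, stopping and terminal decision rules. The paragraph headed Stopping and Decision rule is therefore the place to look up when the trial stops. Its first sentence accepts a difference of 4 or more in the tallies "if this occurs at or before 60 patients" have had outcomes observed, and selects the arm with the larger tally at that time.

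Two later sentences in the same paragraph bear on timing:
- "we will not stop the procedure and make a decision before the outcomes of the first 60 patients have become available"
- Truncation at 100 patients applies "if the criterion for stopping has not been reached at or before 100 outcomes have been observed".

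Other parts of Section VIII also speak to timing:
- **General Design:** "the selection criteria will not be applied until 60 patients have been observed".
- **Study Implementation:** "The data will be examined each time a pair of patients completes follow-up after 60 patients have been observed".
- **Sampling rule:** pairs are formed after randomization "if the stopping criterion is not reached at the time that first 60 outcomes have been observed".
- **Table 1, all three scenarios:** "criterion for stopping is a difference of 4 between the tallies, truncation at 100 patients, minimum # of patients before possible selection=60".
- **Likelihood-ratio section, for a stop at 60:** the case where the difference in "success tallies is exactly equal to 4 (the minimum given the design") is worked through.
- **Minimizing Selection Bias:** efficacy outcomes are not compared within the first 30 pairs, and enrolment goes on only if the difference from those pairs is below 4.

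**The concern.** The criterion sentence departs from the rest of the plan in two ways.

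1. It counts a lead of 4 that was reached before 60 and had shrunk by 60. Elsewhere the criterion is judged on the tallies at 60.
2. It does not count a lead first reached after 60. Elsewhere the data are examined after each later pair, and the criterion can be met up to 100.

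The sentence barring a decision before 60 fixes only the earliest decision time. It does not require the lead to be present still at 60, and it does not make later leads count.

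A DSMB statistician or programmer would take the rule from this paragraph. If the trial stopped at, say, 70 patients, one could argue that the pre-specified criterion did not cover that stop. The plan's likelihood-ratio formula also depends on the answer: it uses exponent 4 when the trial ends on the criterion and the final difference in tallies when it is truncated.

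**Working it through.** **Inputs.** From Table 1 and Section VIII: success probabilities 0.35/0.20, 0.30/0.20 and 0.20/0.20; lead of 4; first decision at 60 patients (30 per arm); truncation at 100 (50 pairs). Assumptions: 1:1 pairs, independent outcomes, ties at truncation split equally.

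**Model.** The difference in tallies is a random walk over pairs. It moves +1 with probability p1(1−p2), −1 with probability p2(1−p1), and otherwise stays put.
- Scenario 1: +1 with 0.35×0.80 = 0.28; −1 with 0.20×0.65 = 0.13; no change 0.59.
- Scenario 2: 0.24, 0.14, 0.62.
- Scenario 3: 0.16, 0.16, 0.68.

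The distribution is carried forward exactly, pair by pair.

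**Step 1: reproduce Table 1.** Rule used: stop if the current absolute difference is at least 4 at pair 30 or at any later pair; truncate at pair 50. Each cell is computed / printed.

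| Scenario | Expected size | Correct selection | Truncation | Stop at 60 |
|---|---|---|---|---|
| 0.35/0.20 | 68.4 / 68.4 | 95.2% / 95.1% | 10.4% / 10.2% | 62.6% / 62.6% |
| 0.30/0.20 | 73.9 / 74.0 | 87.3% / 87.1% | 21.3% / 21.5% | 46.6% / 46.6% |
| 0.20/0.20 | 83.0 / 83.0 | 50.0% / 50.2% | 43.4% / 43.5% | 25.6% / 25.7% |

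The gaps are at most 0.2 percentage points. The plan used 100,000 replications, so the standard error of, for example, the 10.2% is √(0.102×0.898/100,000) ≈ 0.1 point. Table 1 fits this rule.

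**Step 2: try the other readings at 0.35/0.20.** Where an early lead counts, the selected arm may be the first to lead by 4 or the one ahead at 60. This gives five alternatives.

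| Reading | Expected size | Stop at 60 | Run to 100 | Correct selection |
|---|---|---|---|---|
| Current lead at 60 only, nothing until 100 | 74.9 | 62.6% | 37.4% | 95.3% |
| Any lead by 60 counts, then each later pair | 66.3 | 73.9% | 8.0% | 93.9% (first to lead) or 94.3% (ahead at 60) |
| Any lead by 60 counts, nothing later until 100 | 70.4 | 73.9% | 26.1% | 93.9% or 94.3% |

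None matches the printed 68.4, 62.6% and 10.2%.

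**Step 3: how often later leads matter.** Share first meeting the criterion after 60 under the intended rule = 1 − P(stop at 60) − P(truncation):
- Scenario 1: 1 − 0.6263 − 0.1036 = 27.0%
- Scenario 2: 1 − 0.4661 − 0.2130 = 32.1%
- Scenario 3: 1 − 0.2564 − 0.4335 = 31.0%

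If a current lead counted at 60 but not afterwards, all trials not stopped at 60 would run to 100. Expected size = 60×P(stop at 60) + 100×P(run to 100):
- Scenario 1: 60×0.6263 + 100×0.3737 = 74.9
- Scenario 2: 60×0.4661 + 100×0.5339 = 81.4
- Scenario 3: 60×0.2564 + 100×0.7436 = 89.7

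**Step 4: how often an early lead would be lost.** P(lead of 4 ever reached by 60) − P(lead of 4 present at 60):
- Scenario 1: 73.89% − 62.63% = 11.3%
- Scenario 2: 60.73% − 46.61% = 14.1%
- Scenario 3: 40.07% − 25.64% = 14.4%

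A simulation of 400,000 trials gave 11.3%, 14.2% and 14.5%. These figures assume ordered 1:1 pairs before 60, which the plan does not form, so they are illustrative only.

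**The case against.** The strongest reply is that the paragraph largely corrects itself. The truncation sentence presupposes that the criterion can be met between 60 and 100, and the other timing statements listed above point the same way. A stop would be missed only if someone looked after each pair, saw a lead of 4 and ignored it. The early-lead problem could hardly arise, because efficacy comparisons are barred in the first 30 pairs and no ordered pair tally exists before 60. Correct selection stays above 90% at the design alternative under every reading, and nothing shows the rule being misprogrammed.

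Much of this stands. A careful reader can work out the intended rule. The lost-lead shares should carry little weight. The 27.0% to 32.1% figures show how often the intended rule stops after 60; they are not a probability of error. What remains is that the sentence defining the criterion says something different, and no sentence in that paragraph states the rule after 60 positively. A pre-specified stopping rule should not have to be inferred from a truncation clause and other sections.

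**Conclusion.** The inconsistency is real, and it lies in the sentence that defines the decision rule. Followed literally, that sentence would not deliver Table 1. Its practical reach is the roughly 27% to 32% of trials that would first meet the criterion after 60. The design guarantee is not lost and Table 1 is sound for the intended rule, so this should be fixed as wording rather than treated as a design flaw. The figures rest on independent outcomes (no ICU clustering), exactly 30 patients per arm at 60, and equal splitting of ties.

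**What to change.** Replace the criterion sentence with one along these lines: *The trial stops when the current difference between the success tallies is 4 or more, assessed once 60 patients (30 per arm) have been observed and again after each subsequent completed pair, to a maximum of 100 patients.* This also settles that monitoring is by pair; General Design speaks of updating the tallies after each patient. The cost is one sentence: no patients, no further analysis, no new simulation and no change to Table 1 on this account.

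Two related discrepancies need separate work, which this sentence does not cover. The Estimated Sample Size entry allows up to 150 subjects. The narrative after Table 1 (82.5% stopping with 30 per arm, truncation 3.5% to 10.6%, selection at exactly 100) disagrees with the table it describes. The same calculation with a minimum of 100 and truncation at 150 gives 82.5% stopping at the minimum in scenario 1 and truncation of 3.5% and 10.7% in scenarios 1 and 2. That narrative therefore appears to belong to a different design and should be reconciled with the 60/100 rule.

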Design	
To avoid bias in statistical inference due to bias in sampling, only the first 60 patients will be included in this set of analysis. Details explain why bias occurs and how it will affect the statistical inference can also be found in the supplemental appendix. We will use the data from these 60 patients to generate the proportions of patients with the events specified as primary and secondary outcomes. We will also report the descriptive statistics (mean, median, interquartile range) for the time to ICU discharge. Graphical display of the data will be done as well. To compare the intervention effect between the two study groups on the primary and secondary outcomes, we will use generalized linear model with identity link function for continuous variables and logit link function for

	
dichotomous variables following the intent-to-treat principle. Covariates in these models include intervention group indicator, ICU indicators, and the potential confounding factors. The pre-specified potential confounders are age, sex, weight, estimated glomerular filtration rate (eGFR), concomitant treatment with an IL-6 inhibitor, and concomitant treatment with corticosteroids. Generalized estimating equations methodology will be employed to account for the within-ICU correlation for subject assignment to the same ICU area. The key parameter of interest is the regression coefficient corresponding to the intervention group indicator which is the mean difference for continuous outcomes and log-odds ratio for dichotomous outcomes and it represents intervention effect of intermediate-dose anticoagulation compared with that of prophylactic anticoagulation. To report the trial findings, we will present the mean difference and odds ratio when appropriate and their corresponding p-values and 95% confidence intervals. Several pre-specified sensitivity analyses will be conducted: (1) excluding the patients who undergo CRRT during the study period; (2) excluding patients who experienced deviation in anticoagulation from randomized treatment arm; (3) analyzing the patients as the treatment they actually received. Additional sensitivity analysis will also be conducted to include covariates found imbalanced between the two intervention groups.

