Secondary Endpoints	
 Composite of being alive and without clinically-relevant venous or arterial thrombotic events at discharge from the hospital (without transfer to a palliative care unit/hospice) or at 30 days (if hospital stay lasted 30 days or longer) Individual components of the primary outcome in the ICU ICU length of stay Need for renal replacement therapy Major bleeding (assessed by BARC criteria, also explored by ISTH and TIMI criteria) Individual components of the primary outcome during entire hospitalization. Hospital length of stay
Estimated Sample Size	Up to 150 subjects (to be determined by sequential randomized selection design)

[figure not shown]
¹This dose generally does not require routine monitoring of anti-Xa activity, but may be monitored by the primary team outside this study to assess for effectiveness and dose adjusted in consultation with pharmacist

²To be monitored at least 8 hours after the initiation of the infusion or any dose change.

Patients with improving kidney function or new AKI can be switched from one agent to the other within the same intervention group

Acute kidney injury defined as:

- Increase in SCr by ≥ 0.4 mg/dL within 48 hours; or
- Increase in SCr to ≥ 1.5 times baseline, which is known or presumed to have occurred within the prior 7 days; or
- Urine volume <40 mL/h for 6 hours

I. Study Population

Patient Inclusion Criteria	
 • Age >18 years of age • Confirmed diagnosis of COVID-19 by RT-PCR • New admission to eligible CUIMC ICUs within 5 days 
 ○ Transfer from nonparticipating to participating ICU is eligible if otherwise meets eligibility criteria. ○ Patients not on therapeutic anticoagulation and who were already admitted to participating ICU within 5 days of trial initiation are additionally eligible.

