If at the time of stopping there are partially filled or partially observed pairs of patients that have been randomized and have started their intervention, we will allow each patient in each such pair to complete their follow-up even if the arm to which they were randomized is eliminated.

Operating characteristics: In Appendix, we calculate the operating characteristics for various scenarios via simulation study with 100,000 replications. Operating characteristics include the probability of correction, the expected total number of patients, the expected total number of patients with bad outcome, the probability that the trial will be truncated before reaching the criterion for stopping, the probability of reaching a decision after exactly 60 patients (30 in each arm), the probability of correct selection after exactly 60 patients (30 in each arm), and the conditional probability that correct selection is made given that exactly 60 patients (30 in each arm). Scenarios discussed cover the parameters in the preference zone, in the indifference zone, and the null case (i.e., $p_1=p_2$).

Analysis of the Primary Endpoint with the Full Sample

In general, a selection procedure, unlike a hypothesis test procedure, is not specifically designed to provide a *p*-value below a conventional level of significance. Indeed, we will *not* be declaring any differences statistically significant, as that is explicitly *not* the goal of the present selection trial, i.e., we are explicitly *not interested* in testing the null hypothesis of no differences between the interventions. Instead, because the adaptive sequential selection procedure can be described as a procedure that samples until there is a pre-specified *weight of evidence* for making correct selections, assuming there is a minimum true degree of superiority as measured by the design odds

ratio, we will quote the *likelihood ratio (LR) measure of weight of evidence* in various ways. Details regarding how the LR was calculated and examples to illustrate their interpretations can be found in the supplemental appendix.

Endpoint Evaluation

All patients will be evaluable for ischemic outcomes and bleeding from the time of their first treatment with the anticoagulant.

Analysis of Primary Endpoint and Secondary Endpoints for the first 60 patients

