To avoid bias in statistical inference due to bias in sampling, *only* the first 60 patients will be included in this set of analysis. Details explain why bias occurs and how it will affect the statistical inference can also be found in the supplemental appendix. We will use the data from these 60 patients to generate the proportions of patients with the events specified as primary and secondary outcomes. We will also report the descriptive statistics (mean, median, interquartile range) for the time to ICU discharge. Graphical display of the data will be done as well. To compare the intervention effect between the two study groups on the primary and secondary outcomes, we will use generalized linear model with identity link function for continuous variables and logit link function for dichotomous variables following the intent-to-treat principle. Covariates in these models include intervention group indicator, ICU indicators, and the potential confounding factors. The pre-specified potential confounders are age, sex, weight, estimated glomerular filtration rate (eGFR), concomitant treatment with an IL-6 inhibitor, and concomitant treatment with corticosteroids. Generalized estimating equations methodology will be employed to account for the within-ICU correlation for subject assignment to the same ICU area. The key parameter of interest is the regression coefficient corresponding to the intervention group indicator which is the mean difference for continuous outcomes and log-odds ratio for dichotomous outcomes and it represents intervention effect of intermediate-dose anticoagulation compared with that of prophylactic anticoagulation. To report the trial findings, we will present the mean difference and odds ratio when appropriate and their corresponding p-values and 95% confidence intervals. Several pre-specified sensitivity analyses will be conducted: (1) excluding the patients who undergo CRRT during the study period; (2) excluding patients who experienced deviation in anticoagulation from randomized treatment arm; (3) analyzing the patients as the treatment they actually received. Additional sensitivity analysis will also be conducted to include covariates found imbalanced between the two intervention groups.

Operating characteristics of the Study Design

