While the primary aim for the study is to select the best intervention from the 2 candidates, we are also interested in conducting point estimation and hypothesis test for the primary and secondary outcomes when appropriate and to conduct such analysis, *only* the first 30 pairs of patients can be included. This is because we will *not* enroll any additional patients if decision can be made based on the data from the first 30 pair of patients. In other words, the enrollment of 31st pair of patients and thereafter will not be necessary *unless* we don't have sufficient evidence (i.e., the difference in number of "good" outcomes is less than 4) to demonstrate one intervention is better than the other from the outcomes obtained from the first 30 pairs. Therefore, when we have to continue sampling (after the first 30 pairs) until a winner appears and use the entire sample to construct the analysis, two consequences will occur: (1) from point estimation standpoint, the probability of "good" outcome for the winner will be over-estimated (and for the loser will be under-estimated); and (2) from hypothesis testing standpoint, as sampling plan "enforces" the data to support the alternative hypothesis, bias then introduced against the null.

Nevertheless, to prevent any bias due to sampling, we propose to recruit the first 30 pairs without any look and/or comparison of their primary and secondary efficacy outcomes (unless the early stopping is required from the recommendation of DSMB due to safety concern). In such case, the recruitment of first 30 pairs of patients is independent of their outcome as we usually do for any fixed sample size design. Thus, conducting point estimation (together with a 95% confidence interval) and hypothesis testing with those 60 patients is entirely appropriate (i.e., can be done unbiasedly).

VII. References

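### Major bleeding is compared between arms only in the first 60 patients, although bleeding does not drive stopping

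*Combined protocol and SAP*

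**What the plan says.** The Design row of the protocol outline states that "only the first 60 patients will be included in this set of analysis". Section VIII, under the analysis of primary and secondary endpoints for the first 60 patients, repeats that only "the first 60 patients will be included in this set of analysis" and adds: "We will use the data from these 60 patients to generate the proportions of patients with the events specified as primary and secondary outcomes". The models, p-values, confidence intervals and sensitivity analyses follow in the same paragraph. Major bleeding (BARC, also explored by ISTH and TIMI) is on the Secondary Endpoints list, so it falls inside this set.

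The reason is given under Minimizing Selection Bias. Pairs after the 30th are enrolled only if the tallies differ by less than 4, so full-sample estimates of the good outcome are biased. For estimation and testing of primary and secondary outcomes alike, the plan concludes that only "the first 30 pairs of patients can be included".

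The one full-sample analysis in Section VIII is the likelihood ratio for the primary endpoint. Endpoint Evaluation, just before the first-60 text, says: "All patients will be evaluable for ischemic outcomes and bleeding from the time of their first treatment with the anticoagulant". No analysis is attached to that sentence.

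**The concern.** The argument under Minimizing Selection Bias concerns an outcome that is counted in the tally. Bleeding is not counted. Its estimate can be distorted by the stopping rule only so far as bleeding goes with a poor primary outcome, and the plan makes no separate case that this matters.

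Bleeding is the first risk listed for the intermediate dose in Section VI. If the trial runs past 60, major bleeds in later patients are missing from the reported comparison and its interval is wider than the data allow. There is also a gap in the decision rule: a tie at truncation is settled on safety and secondary outcomes. A tie can arise only at 100 patients, when the one specified safety comparison omits 40 of them.

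**Working it through.** **Inputs.** From Table 1: first look at 60 patients, stop at a tally difference of 4, truncation at 100, and success probabilities 0.35/0.20, 0.30/0.20 and 0.20/0.20 (scenarios 1 to 3). The documents give no bleeding rate and no link between bleeding and outcome. Assumed here: bleeding risk 5% in good-outcome and 15% in poor-outcome patients, or 2% and 25% for a stronger link, each plus 5 points in the intermediate arm. Patients are taken as independent and clustering is ignored.

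**1. Reproduce Table 1.** At 60 patients the tallies are two independent Binomial(30, p) counts. Each further pair moves the difference up with probability p1(1−p2), down with probability p2(1−p1), and otherwise leaves it unchanged. The trial stops at a difference of 4 or at 50 pairs. Exact recursion gives:

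| Plan / recomputed | Scenario 1 | Scenario 2 | Scenario 3 |
|---|---|---|---|
| Expected N | 68.4 / 68.4 | 74.0 / 73.9 | 83.0 / 83.0 |
| Stops at 60 (%) | 62.6 / 62.6 | 46.6 / 46.6 | 25.7 / 25.6 |
| Truncated (%) | 10.2 / 10.4 | 21.5 / 21.3 | 43.5 / 43.4 |

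The text after the table gives other figures (82.5% stopping at 30 per arm, truncation 3.5% to 10.6%). The recomputation supports the table.

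**2. Share of patients left out.** A trial ending at T patients leaves out (T − 60)/T: zero at 60, and 40/100 = 40% at the cap. Averaged over the exact distribution of T, this is 9.3%, 15.0% and 24.0% in scenarios 1 to 3, before overrun. The ratio of expectations, for example (68.4 − 60)/68.4 = 12.3%, is larger (12.3%, 18.9%, 27.7%) because long trials weigh more in it.

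**3. Cost of using every patient.** Simulation of the same stopping rule (300,000 to 400,000 trials), in percentage points:

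| | Scenario 1 | Scenario 2 | Scenario 3 |
|---|---|---|---|
| Bias in bleeding difference, 5%/15% | −0.14 | −0.15 | 0.00 |
| Bias in bleeding difference, 2%/25% | −0.31 | −0.33 | 0.00 |
| Bias in primary difference | about 1.3 | about 1.4 | 0.0 |
| SD of bleeding difference, first 60 → all (5%/15%) | 9.1 → 8.7 | 9.2 → 8.5 | 9.3 → 8.1 |

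Before rounding, the SD falls by about 5%, 8% and 13%. In the extreme case where every bleed occurs in a poor-outcome patient, with arm rates of 5% to 15%, the bias is still at most about 0.3 points. With equal bleeding rates in that case, a nominal 5% test rejects in 3.3% to 5.6% of trials.

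**4. Precision at the cap.** The Wald 95% half-width is 1.96 × √(2r(1−r)/n) for a common assumed rate r.
- r = 10%, n = 30: 1.96 × √(0.18/30) = 15.2 points.
- r = 10%, n = 50: 1.96 × √(0.18/50) = 11.8 points.
- r = 5%: 11.0 against 8.5 points.

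The ratio is √(30/50) = 0.775 at any rate. It applies only when the trial reaches 100. With about 3 events per arm (30 × 0.10) the Wald form is rough, and it is not the planned adjusted GEE.

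**5. Ties.** The exact probability of a tie at 100 patients is 1.7%, 3.8% and 8.6% in scenarios 1 to 3.

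**The case against.** The first-60 analysis is valid, and there are good reasons to keep it. Those patients are recruited without any look at efficacy, whereas later ones accrue while the tallies are examined pair by pair, and overrun continues after a selection has been made. The simulation models none of that, nor clustering or drift over time. Fatal bleeding is itself a poor outcome, so some link between bleeding and the tally is built in. All this stands. It argues for showing both results, not for leaving the second one out.

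A reader might infer that later bleeds are lost. The documents do not support that: Sections III to V provide for safety surveillance from enrolment, blinded adjudication, and reporting of all events to the DSMB. The bleeds are absent from the planned comparison only.

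A reader might also infer that nothing uses patients after the 60th. That is wrong for the primary endpoint: the likelihood ratio uses the full sample and is repeated with overrun data. The tie rule also lets later safety data inform selection, though without a stated method. Section VIII opens with a general line that analysis will be by intention to treat once the trial is completed. It names no patient set, and the explicit first-60 wording governs the comparisons.

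Finally, a reader might want the restriction lifted for every secondary endpoint. The plan's reason applies directly to components of the primary outcome and carries over to the hospital-discharge composite.

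**Conclusion.** The point holds for major bleeding. No planned between-arm bleeding comparison goes beyond patient 60, and the plan's reason for that limit has little force for an outcome outside the tally.

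The size is moderate. The 40% figure is a ceiling, reached only at truncation; under the design alternative about 63% of trials stop at 60 and lose only overrun. The average gain in SD is 5% to 13%, against a bias of at most about 0.3 points, compared with 1.3 to 1.4 points for the primary difference in scenarios 1 and 2. The stopping figures rest on the plan's own design. The bias and precision figures rest on assumed bleeding rates and independent patients.

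All shares use the cap in Section VIII, "with a maximum of 100 patients". The outline's Estimated Sample Size row says up to 150. If that were the cap, the ceiling would be 90/150 = 60%; the two entries need reconciling.

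This is a cheap improvement, not a flaw that invalidates the planned analysis.

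**What to change.** In the Design row, the first-60 analysis in Section VIII, and Minimizing Selection Bias, add wording such as: major bleeding (BARC 3 or 5, ISTH, TIMI) is also compared by assigned arm in all enrolled patients, including overrun, with a confidence interval, and is shown beside the first-60 result. Tie Endpoint Evaluation to this analysis, so that its sentence on evaluable patients and the first-60 rule no longer pull apart.

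Keep the first-60 restriction for the primary endpoint and for secondary endpoints that are its components.

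The cost is SAP wording and a few extra tables. The downside is a possible bias of a few tenths of a point in the all-patient bleeding difference, which can be stated in a footnote and judged against the first-60 figure next to it.
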